Objective: To evaluate whether discontinuation of VKAs results in a higher vitamin K status and deceleration of the rate of mature cross-linked elastin degradation.

Study design: Observational study.

Study population: A total of 30 VKA users who will discontinue the use of VKAs.

Main study parameters/endpoints: The primary endpoint is the change in the rate of elastin degradation quantified by the plasma desmosine assay. Secondary endpoints are the change in vitamin K status quantified by measuring plasma levels of dephosphorylated uncarboxylated, (i.e. dp-uc, inactive) Matrix Gla Protein (MGP), the relation between desmosine and dp-ucMGP and differences of desmosine and dp-ucMGP levels among subjects with different polymorphisms of the vitamin K 2,3-epoxide reductase complex 1 (VKORC1) gene.

Nature and extent of the burden and risks associated with participation, benefit and group relatedness: We will draw extra blood collection tubes at two moments. The first time is during one of the last regular INR testing at the anticoagulation clinic, therefore no additional venipuncture has to be performed. At this moment two additional blood collection tubes will be drawn. The second moment is approximately 6 months after discontinuation of VKAs. At this point the patient will undergo an additional venipuncture. Patients are asked to

Version number: 4.0, August 2017

fill in a questionnaire concerning age, gender, length, height, indication for VKA use, duration of VKA use, smoking status and history, presence of COPD and other pulmonary disease, whether patients will switch to DOACs or will completely stop the use of anticoagulants, vitamin D supplementation, use of multivitamins and use of medications. Furthermore, we will record the INR at baseline. Participants may experience some discomfort during blood sampling. Participating in the study has negligible risks.

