3. STUDY DESIGN

The study is designed as a non-interventional study. The follow up per patient comprises 6 months. We will include 30 VKA users who will stop the use of VKAs. At baseline, patients are asked to fill in a questionnaire and two additional samples of blood are taken during the regular testing of the international normalized ratio (INR). One blood sample is needed for determination of the VKORC1 polymorphisms and one for desmosine and dp-ucMGP levels. After 6 months, patients are asked to draw one additional blood sample for determination of desmosine and dp-ucMGP. At baseline and 6 months blood can be drawn in the Canisius Wilhelmina Hospital or one of the outposts of the anticoagulation clinic. Since the blood samples have to be stored and frozen in the laboratory in the Canisius Wilhelmina hospital within 2 hours after drawing, patients can visit the outposts within one hour before the blood samples are transported to the laboratory, i.e. within one hour before closing the outpost. If both visiting the hospital or outpost is not possible, the patient can contact the investigator to make an appointment for drawing the blood samples at home.

An overview of is given in Figure 1.

Figure 1. Overview of study and time schedule

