5. METHODS

5.1 Study parameters/endpoints

5.1.1 Main study parameter/endpoint

The primary endpoint is the difference in elastin degradation rate, quantified by the change in plasma desmosine levels, measured at baseline and 6 months after discontinuation of VKAs.

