5.1.3 Other study parameters

In addition, the following parameters will be registered, because of their possible confounding capacity:

- Gender
- Age
- INR
- Indication for VKA use
- Duration of VKA use
- BMI
- Smoking status and history
- Presence of COPD
- Presence of other pulmonary disease
- Medication
- Vitamin D supplementation
- Use of multivitamins
- Switch to DOACs or complete discontinuation of anticoagulant use

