7. STATISTICAL ANALYSIS

7.1 Primary study parameter(s)

The primary endpoint is the change in plasma desmosine levels. Plasma desmosine levels will be determined at baseline and 6 months after discontinuation of VKAs. Univariate analysis (ANCOVA) will be used for comparing plasma desmosine levels before and after discontinuation of VKAs. Results will be corrected for the following covariates (if statistical significant): age, gender, INR, indication for VKA use, duration of VKA use, BMI, smoking status and history, presence of COPD or other pulmonary disease, vitamin D supplementation, use of multivitamins and use of medication. A *P*<0.05 will be considered statistically significant. Statistics will be performed using SPSS (SPSS Inc., Chicago, Illinois, USA).

Both desmosine and dp-ucMGP levels will be log-transformed before performing statistical analysis.

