7.2 Secondary study parameter(s)

The change in plasma dephosphorylated uncarboxylated matrix Gla-protein at baseline and 6 months after discontinuation of VKAs will be a secondary study parameter. Univariate analysis (ANCOVA) will be used, corrected for the following covariates (if statistical significant): age, gender, INR, indication for VKA use, duration of VKA use, BMI, smoking status and history, presence of COPD or other pulmonary disease, vitamin D supplementation, use of multivitamins and use of medication. Univariate analysis will be used to assess the relationships between dp-ucMGP and desmosine and Pearson's rho will be calculated. To assess the differences of both pDES and d-ucMGP levels between the various VKORC1 polymorphisms, univariate analysis will also be used, corrected for the same covariates as listed above.

Both desmosine and dp-ucMGP levels will be log-transformed before performing statistical analysis.

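### Sections 7.1 and 7.2 adjust the before/after comparison only for covariates that prove significant; relative to a paired test this cannot improve the estimated mean change, and its effect on the P value depends on a model the plan does not specify

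*Combined protocol and SAP*

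**What the plan says.** The endpoint in section 5.1.1 is the difference in elastin degradation rate, "quantified by the change in plasma desmosine levels, measured at baseline and 6 months after discontinuation of VKAs". There is one group and no comparator: "We will include 30 VKA users who will stop the use of VKAs" (section 3).

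Section 7.1 compares desmosine before and after discontinuation by a univariate ANCOVA on the log scale at P<0.05, and adds: "Results will be corrected for the following covariates (if statistical significant". The list has 11 entries, or 13 if smoking status/history and COPD/other pulmonary disease are each split. Section 7.2 applies the same rule to dp-ucMGP: "Univariate analysis (ANCOVA) will be used, corrected for the following covariates (if statistical significant".

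Section 5.1.3 gives the reason for collecting these variables: "the following parameters will be registered, because of their possible confounding capacity". They are single baseline values: "At baseline, patients are asked to fill in a questionnaire" (section 3) and "Furthermore, we will record the INR at baseline" (Summary). One registered variable, "Switch to DOACs or complete discontinuation of anticoagulant use", is not in the 7.1 list.

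Neither section states whether the outcome is a level or a change, how the two samples from one patient are linked, what a covariate must be significantly related to, or whether covariates are centred. No unadjusted paired test is named.

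**The concern.** The stated purpose of the adjustment is confounding, but the contrast is within patients. Age, sex or baseline INR is the same number on both sides of each patient's comparison. It may explain why some patients change more than others, but it cannot bias the average change. The adjustment therefore does not do the job it is given.

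Choosing covariates by their P values in the same 30 patients brings a second problem. A covariate kept because it happens to fit the change lowers the residual variance, and so the reported standard error, while the true sampling variability of the mean change stays the same. At stake is the meaning of P<0.05 on the primary endpoint and on the dp-ucMGP endpoint. Because the model is not fixed, two analysts could follow section 7.1 and obtain tests with clearly different error rates.

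**Working it through.** The plan gives no power, SD, correlation or error rate beyond P<0.05, so there is no figure to reproduce. Inputs from the documents: 30 patients (section 3), 11 or 13 candidates (section 7.1), 0.05 (section 7.1). Assumed: two-sided tests, complete pairs, independent covariates with one df each, within-patient correlation ρ, and the share R² of variance that a covariate explains.

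**1. The estimate does not move.** Let D be a patient's log change and fit D = α + β(x − x̄) + e. The intercept's normal equation is Σ(D − α̂) − β̂Σ(x − x̄) = 0. The second sum is zero, so α̂ is the plain mean of D whatever covariates are in the model. Simulated data agree to about 3×10⁻¹⁶.

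**2. Noise covariates are often kept.** Chance of at least one: 1 − 0.95¹¹ = 43.1%; 1 − 0.95¹³ = 48.7%. Simulation with one-at-a-time screening on change: 42.9-48.8%.

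**3. Type I error by reading** (simulated at n=30, nominal 5%):

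| Reading | Type I error |
|---|---|
| Unadjusted paired test | 4.8-5.3% |
| Paired model, covariate main effects only | same as the paired test |
| Change model, centred, screened on change, null covariates | 5.9-7.1% |
| Same, one covariate with R² = 0.2 | 8.7-9.4% |
| Same, one covariate with R² = 0.4 | 13.2-14.2% |
| Change model, centred, screened on baseline or mean level | 4.8-5.5% |
| 60-row ANCOVA on levels, pairing ignored, screened on level, ρ = 0.3 | 2.2-5.1% |
| Same, ρ = 0.7 | 0.6-2.6% |

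The spread in the change-model rows covers univariable, forward and backward selection; the null row also covers 11 and 13 candidates, with ρ = 0.5 and 0.8 for the univariable screen.

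In one simulated data set the paired test and the random-intercept model, with or without three covariates, all gave −0.34694 (SE 0.13872). The centred change model gave the same estimate with SE 0.13221, a ratio of 0.13221/0.13872 = 0.953.

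**4. Why the change model runs high.** After screening null covariates on change, the mean SE is 0.951-0.959 of its proper value. The critical t on 28 df is 2.048; 2.048 × 0.951 = 1.95 and 2.048 × 0.959 = 1.96, which give P = 6.1% and 5.9%, in line with the null row.

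If a covariate truly predicts change, the model's SE is too small for the population mean by √(1 − R²), even without selection:
- R² = 0.2: 2.048 × √0.8 = 1.83, P = 7.8% (simulated with that one covariate prespecified: 7.8%).
- R² = 0.4: 2.048 × √0.6 = 1.59, P = 12.4% (simulated: 12.2%).

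Univariable selection adds only 8.7 − 7.8 = 0.9 and 13.2 − 12.2 = 1.0 points. Prespecifying all 11 covariates gives 7.6% and 11.8%. Most of the excess therefore comes from treating covariates as fixed.

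**5. Why the 60-row model runs low.** It takes the variance of the difference as 2σ²/n when it is 2σ²(1 − ρ)/n. Without covariates the effective cut-off is 2.002/√(1 − ρ): 2.39 at ρ = 0.3 (1.7%), 2.83 at 0.5 (0.5%) and 3.66 at 0.7 (0.03%). Covariates that predict level remove part of the ignored between-patient variance. With ρ = 0.5, two covariates explaining 30% of level variance and a true change of 0.53 SD, power is about 53% unadjusted, 71% after selection and 80% for the paired test.

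**The case against.** The strongest objection is that section 7.1 speaks of comparing levels by a univariate ANCOVA, so its most literal reading is the 60-row model. There the selection rule is not anti-conservative in general, and it raises power (53% to 71% in the case above). A reader might infer that the rule has no upside, or that at best it leaves a paired test unchanged. The documents do not support that, because they never name a paired test. This part of the objection stands. Even so, selection only recovers some of what pairing gives outright, and power stays below 80%.

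A reader might also infer a false-positive rate of 20% or more. That figure arises if covariates screened on change are entered uncentred, so that the intercept refers to a patient with age zero and BMI zero. Sections 5.1.1 and 7.1 define the target as the before/after change, so this would be a misapplication of the plan. Its size also rests wholly on invented covariate distributions: 20-22% under one set, 29% under another. It is a trap to avoid, not a measure of severity.

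Three further points have weight. With null covariates the inflation is only one to two points. If the target were the change at this sample's own covariate means, prespecified adjustment would be valid and could be more precise; selection would still not be. And sections 5.3 and 5.4 foresee withdrawals and replace at most five patients, so the exact equality in step 1 holds only for complete pairs.

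Pilot status explains why section 4.4 has no sample size calculation. It does not explain an open-ended model behind a P<0.05 test on a primary endpoint.

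**Conclusion.** The point holds in this form. The significance condition cannot improve the estimated mean change relative to a paired test and does not address confounding, since fixed baseline values cannot confound a within-patient change. Its effect on the test is undetermined because the model is undetermined: unchanged at 5%, about 6-7% (9-14% with a strongly predictive covariate), or about 1-5% with a loss of power. The documents do not establish that the primary test is inflated as planned, and selection is not the main source of the larger figures.

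These sizes rest on n=30 complete pairs, two-sided tests, independent covariates and assumed ρ and R². The equality of adjusted and unadjusted mean change needs only complete pairs and centring. The VKORC1 comparisons in section 7.2 are between patients and are not covered here. Severity is minor to moderate: an observational pilot, but a cheap correction to its primary analysis.

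**What to change.** In section 7.1, and in section 7.2 for dp-ucMGP:

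- Name the unadjusted paired test of the within-patient log change as the main analysis.
- Delete the significance condition, and the selection it implies, for this comparison. Deleting it alone is not enough: a fixed covariate list does not restore 5% for the population mean change when a covariate predicts change (step 4).
- If an adjusted model is wanted, specify it as a sensitivity or descriptive model of the log change, with a short, mean-centred covariate set that the sponsor fixes in advance and keeps whatever the P values. The sponsor may wish to consider the DOAC-switch variable, which is registered in 5.1.3 but not listed in 7.1.
- State that this model describes how the change varies between patients, and that its intercept P value does not replace the paired test.

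The cost is wording only, with no extra data, visits or assays. The downside is that the other listed covariates become descriptive for the before/after comparison, and the sensitivity model uses a few degrees of freedom.

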7.2 Secondary study parameter(s)

The change in plasma dephosphorylated uncarboxylated matrix Gla-protein at baseline and 6 months after discontinuation of VKAs will be a secondary study parameter. Univariate analysis (ANCOVA) will be used, corrected for the following covariates (if statistical significant): age, gender, INR, indication for VKA use, duration of VKA use, BMI, smoking status and history, presence of COPD or other pulmonary disease, vitamin D supplementation, use of multivitamins and use of medication. Univariate analysis will be used to assess the relationships between dp-ucMGP and desmosine and Pearson's rho will be calculated. To assess the differences of both pDES and d-ucMGP levels between the various VKORC1 polymorphisms, univariate analysis will also be used, corrected for the same covariates as listed above.

Both desmosine and dp-ucMGP levels will be log-transformed before performing statistical analysis.

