1. INTRODUCTION AND RATIONALE

Elastin is a unique protein providing elasticity, resilience and deformability to dynamic tissues, such as lungs and vasculature.¹ Elastin fibers are almost exclusively developed before birth and in the first period of life after which the synthesis of elastin is suppressed at a post-transcriptional level.¹ Elastin can be degraded by certain proteases, also referred to as elastases.¹ Elastin has high affinity for calcium,¹ and the calcium content of elastin fibers therefore increases during aging.² Calcium changes the conformation of elastin, which gives elastases access to elastin fibers leading to degradation.^{3,4} In turn, partially degraded elastin has a higher affinity for calcium due to increased polarity.⁴ Therefore, elastin calcification and elastin degradation are two pathologic processes that stimulate each other. When elastin is degraded, desmosine, a component of mature elastin, can be detected in the bloodstream. Since desmosine is only found in mature elastin, its plasma levels are a reflection of the rate of systemic elastin degradation.⁵

Chronic obstructive pulmonary disease (COPD) is characterized by a disturbed balance between proteases and anti-proteases, resulting in an accelerated degradation of elastin in the lungs, but also in blood vessels.⁶ Besides elastin degradation, calcification of elastin, i.e. in coronary arteries, is also accelerated in patients with COPD.⁷

Matrix Gla protein (MGP) is a potent inhibitor of elastin calcification and needs vitamin K to become activated. In an observational epidemiological study, higher vitamin K2 intake was associated with less vascular calcification.⁸ In addition, three years of vitamin K2 supplementation in postmenopausal women resulted in a decrease of arterial stiffness, while an increase was observed in the placebo group.⁹ The dephophorylated uncarboxylated (i.e. inactive) form of MGP, dp-ucMGP, can be measured in plasma and its levels are negatively associated with vitamin K status. Therefore, dp-ucMGP levels are used as a measure for vitamin K status.

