Earlier, we found a reduced vitamin K status in patients with COPD compared with patients without COPD and an inverse association between vitamin K status (quantified by dp-ucMGP levels) and elastin degradation (quantified by desmosine levels) among COPD patients (abstract ATS 2016). Recently, in 106 VKA users we found higher desmosine and dp-ucMGP levels when compared with patients who do not use VKAs. In VKA users, we also found an inverse association between vitamin K status and elastin degradation (quantified by plasma dp-ucMGP and desmosine levels, respectively).

During activation of vitamin K dependent proteins such as MGP, vitamin K is oxidated from vitamin K 2,3-epoxide to vitamin K hydroquinone. Subsequently, vitamin K 2,3-epoxide needs to be recycled to the quinone form by an enzyme called vitamin K 2,3-epoxide reductase complex 1 (VKORC1). Different single nucleotide polymorphisms of this gene exist, each resulting in a different level of expression of the enzyme. Since the VKORC1 enzyme is the direct pharmacologic target of VKAs, this gene is for an important part responsible for the interindividual dose variability of VKAs. The rs9923231 SNP (g.-1639G.A) is the main genetic determinant of VKA dose requirement and can alone explain between 25% to 30% of the dose variance among patients.¹⁰

Nowadays, oral anticoagulants exist which do not influence vitamin K status, the so-called direct oral anticoagulants (DOAC). An increasingly number of patients is switching from VKAs to DOACs.

We hypothesize that discontinuation of VKAs results in an improved vitamin K status and a deceleration of elastin degradation. In order to test this hypothesis, we want to conduct an observational pilot study in which the change in elastin degradation– quantified by plasma desmosine concentrations – in patients who discontinue use of VKAs will be used as primary endpoint.

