4.4 Sample size calculation

It concerns a pilot study and therefore sample size calculation was not performed.

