5.1.2 Secondary study parameters/endpoints

Secondary endpoints are:

- The difference in vitamin K status, quantified by the change in dp-ucMGP, measured at baseline and 6 months after discontinuation of VKAs.
- The association between desmosine and dp-ucMGP in patients who use VKAs and do not use VKAs.
- Differences in desmosine and dp-ucMGP levels between different VKORC polymorphisms.

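### Section 7.2 specifies no covariate correction for the desmosine/dp-ucMGP association, although the protocol links COPD to both markers and registers COPD and age as possible confounders

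*Combined protocol and SAP*

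**What the plan says.** Section 5.1.2 lists as a secondary endpoint "The association between desmosine and dp-ucMGP in patients who use VKAs and do not use VKAs". In this single cohort that means the relation at baseline (on VKA) and at 6 months (off VKA).

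Section 7.2 describes three analyses:

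- **Change in dp-ucMGP:** ANCOVA, corrected for a list of covariates that includes age and COPD, each kept only if significant.
- **Relation between the two markers:** "Univariate analysis will be used to assess the relationships between dp-ucMGP and desmosine", with Pearson's coefficient. No covariates are mentioned.
- **VKORC1 comparisons:** corrected for the same list.

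Both markers are log-transformed.

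The background bears directly on this. The Introduction describes the protease imbalance of COPD as "resulting in an accelerated degradation of elastin in the lungs, but also in blood vessels", and reports that "we found a reduced vitamin K status in patients with COPD compared with patients without COPD". Lower vitamin K status means higher dp-ucMGP. Section 5.1.3 says that "the following parameters will be registered, because of their possible confounding capacity", and its list contains age and presence of COPD. Sections 4.2 and 4.3 neither require nor exclude COPD, so the sample can contain patients with and without it.

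**The concern.** A within-patient change largely cancels stable patient characteristics, because each patient is their own comparison. A correlation of levels across patients does not. As written, section 7.2 states a correction where stable confounders matter less and states none where they matter more.

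If patients with COPD tend to have both higher dp-ucMGP and higher desmosine, mixing them with patients without COPD produces a positive correlation even if neither marker affects the other. Age could do the same: the Introduction ties it to the calcium content of elastin, although a link between age and dp-ucMGP is an assumption here. The study hypothesis is mechanistic, so a positive coefficient invites a mechanistic reading. The data needed to examine the alternative are already being collected.

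**Working it through.** **Inputs from the documents**

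- Sample size: "A total of 30 VKA users who will discontinue the use of VKAs" (Summary).
- Power: none stated. "It concerns a pilot study and therefore sample size calculation was not performed" (section 4.4).
- Threshold: a P value below "0.05 will be considered statistically significant" (section 7.1). I assume that it is two-sided and also applies to secondary tests.

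**Inputs assumed, because the documents give none:** COPD prevalence *p*, the shift *d* in each log marker with COPD (in within-group SD, equal for both markers), and the correlation of age with each marker. The plan has no figure of its own to reproduce.

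**Step 1: the correlation needed for significance.** With n = 30 and t(0.975, 28) = 2.048, the critical |r| = t/√(28 + t²) = 2.048/√(28 + 4.196) = 0.361.

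**Step 2: the correlation induced by COPD alone, with no direct link.** r = p(1−p)d² / [1 + p(1−p)d²].

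- COPD 15%, d = 0.5: 0.1275 × 0.25 = 0.032, so r = 0.032/1.032 = 0.03.
- COPD 20%, d = 1: 0.16 × 1 = 0.16, so r = 0.16/1.16 = 0.14.

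**Step 3: adding age, correlated 0.4 with each marker within COPD groups.** The result depends on which SD the COPD shift is measured in.

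- Shift of 1 total within-group SD: age accounts for 0.4² = 0.16 of a within-group variance of 1, so r = (0.16 + 0.16)/1.16 = 0.28.
- Shift of 1 SD of what remains after age: age adds 0.16/0.84 = 0.190, so r = (0.16 + 0.190)/(1 + 0.16 + 0.190) = 0.26.

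**Step 4: chance of a significant crude correlation** (simulated samples of 30, no direct link).

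| Assumed scenario | Induced r | Significant crude r |
|---|---|---|
| COPD 15%, 0.5 SD | 0.03 | about 5% |
| COPD 20%, 1 SD | 0.14 | 11% |
| COPD 20%, 1 SD, plus age 0.4 | 0.26 to 0.28 | 29 to 32% |

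In the first scenario, adding age with a correlation of 0.3 raises the rate to between 9% and 10%.

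**Step 5: COPD alone over a wider range.** For prevalence 10 to 50% the rate is about 5 to 11% with shifts up to 0.8 SD, 7.5 to 18% at 1 SD, and 15 to 52% at 1.5 SD. For the induced r itself to reach 0.361, the shift in both markers must be √[(0.361/0.639)/(p(1−p))]. That is 2.5, 1.9, 1.6 and 1.5 SD at prevalence 10, 20, 30 and 50%.

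**Step 6: the adjusted analysis.** The partial correlation given the simulated confounders rejects in about 5% of samples in every scenario. This holds by construction, since nothing else was simulated. It does not show that age and COPD are sufficient.

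**Step 7: cost in precision.** On the Fisher scale the standard error goes from 1/√27 to 1/√25 with two covariates, a ratio of √(27/25) = 1.039.

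**The case against.** Five points on the other side deserve weight.

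**The wording may not mean unadjusted.** A reader might infer that the plan commits to a crude Pearson correlation. That is the natural reading but not a certain one. The protocol uses the term univariate analysis for its ANCOVA models with covariates, and Pearson's coefficient could be a descriptive companion to such a model. What stands is that this sentence alone mentions neither ANCOVA nor any correction, so the reader cannot tell whether covariates apply.

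**COPD is not shown to be a common cause.** A reader might infer this from the Introduction, but the documents report lower vitamin K status in COPD as an association without direction. The Summary places protease imbalance among the mechanisms by which COPD develops, so COPD could lie downstream of elastin degradation. Adjusting would then weaken a true association. Under one assumed chain of that kind, true correlations of 0.3 to 0.5 fell to partial correlations of about 0.24 to 0.48. This is a reason to show both estimates.

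**Earlier data partly answer the worry.** The Introduction reports the association among COPD patients, where presence or absence of COPD cannot create it. Severity or age still could, and the present sample is not restricted to COPD.

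**The larger rates rest on assumptions.** The 29 to 32% needs a 1 SD shift in both markers and a sizeable age effect on both. COPD alone in the mild case leaves the rate essentially nominal.

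**The stakes are limited.** This is a secondary endpoint, called an association, in a pilot study. No passage says that the coefficient will be read causally. Demoting the crude coefficient to description only would be partly a matter of preference.

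**Conclusion.** The point holds in a limited form. Section 7.2 gives no covariate correction for the cross-sectional association, although it does so for the analyses on either side, and the protocol itself supplies the reasons to consider COPD and age. An unadjusted coefficient may partly reflect either of them.

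How much is unknown. Under the stated assumptions the false-positive rate runs from about 5% to 29 to 32%, with 11% for COPD alone at 20% prevalence and a 1 SD shift. These are illustrations, not estimates for this cohort. A reader might infer that confounding is likely to produce a significant result here; without prevalence or effect sizes, the documents do not support that. The primary endpoint is unaffected. This is a cheap improvement to a secondary analysis.

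**What to change.** In section 7.2, prespecify a partial correlation of log desmosine and log dp-ucMGP, computed separately at baseline and at 6 months. Adjust for age and COPD (yes/no), and keep both whatever their P values. Report it beside the crude Pearson coefficient, each with a 95% confidence interval, and state that the crude coefficient alone will not be read as support for the mechanism.

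The cost is wording only, since both covariates are already collected. There are three downsides:

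- The interval is about 4% wider on the Fisher scale.
- A true association may be attenuated if COPD lies downstream of elastin degradation, which is why both estimates are shown.
- Confounding by other registered factors, such as smoking, may remain and should be acknowledged.
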